Bipolar depression is common and challenging to treat. Brexpiprazole may be a promising treatment for Bipolar Disorder (BPD), which is a severe and persistent psychiatric illness affecting 1.6-3.5% of the population (6, 7). In addition to manic episodes, persons with BPD frequently experience depression. Depression in BPD may be particularly challenging to treat. Findings from the STEP-BD study indicate that bipolar depression may not respond well to selective serotonin reuptake inhibitors, which are a standard treatment for major depressive disorder (MDD) (8). Lamotrigine is commonly prescribed for bipolar depression, but it appears to be more effective than placebo only for severe depression (9). Only three medications (quetiapine, the combination of olanzapine and fluoxetine, and lurasidone) are FDA-approved for bipolar depression. Thus, new, safe, and effective treatments for the depressed phase of BPD are badly needed. Brexpiprazole is a partial agonist at dopamine D2 receptors that is structurally similar to aripiprazole. Data suggest that brexpiprazole is effective both as an adjunct treatment for major depressive disorder (10) and as a treatment for schizophrenia (11), and has FDA approval for both indications.

Given the promising findings in both major depressive disorder and schizophrenia, a proof-of-concept study is proposed to examine the safety and tolerability, as well as efficacy of brexpiprazole in patients with bipolar depression. Depressive symptoms will be assessed using both observer-rated and self-rated depression scales. Manic symptoms and quality of life will also be assessed. Safety and tolerability will be assessed using a side-effects scale as well as standard antipsychotic extrapyramidal symptom rating scales. Cognitive domains relevant to bipolar depression will be assessed. Because bipolar depression is associated with high sensitivity elevated C-reactive protein levels (hs-CRP, an inflammatory biomarker) (12) and data suggest that brexpiprazole decreases hs-CRP levels (13), hs-CRP levels will also be assessed at baseline and exit, and the relationships between changes in these levels and clinical outcomes explored.

3. Concise Summary of Project:

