We will conduct an 8-week, non-randomized, open label study of brexpiprazole in 20 persons with bipolar disorder. Primary Aim will be to determine if brexpiprazole is associated with a reduction in depressive symptom severity using the Montgomery-Asberg Depression Rating Scale (MADRS) in outpatients with bipolar disorder, depressed mood state. Secondary Aims will be: 1) Assess manic symptoms in patients with bipolar disorder receiving brexpiprazole, 2) Assess cognition in patients with bipolar disorder receiving brexpiprazole, 3) Assess the safety and tolerability of brexpiprazole in patients with bipolar disorder, 4) Assess quality of life in patients with bipolar disorder receiving brexpiprazole.

Subjects will be discontinued from the study if any of the following conditions occurs: change in diagnosis to other than bipolar I or II disorder, development of active suicidal or homicidal ideation with plan and intent, worsening in mood symptoms, that in the opinion of the investigators requires discontinuation, pregnancy, development of severe or life-threatening medical condition, involuntary psychiatric hospitalization or incarceration.

4. Study Procedures:

Baseline: This visit will be split into two portions: Baseline 1 and Baseline 2.

For Baseline 1 (~3 hours), the psychiatric diagnosis will be confirmed by the structured clinical interview for DSM-5 (SCID), mood assessed via the Montgomery-Asberg Depression Rating Scale (MADRS), depression via the Inventory of Depressive Symptomatology Self-Report (IDS-SR₃₀), mania via the Young Mania Rating Scale, and quality of life via the Quality of Life in Bipolar Disorder (QOLBD). Blood will be drawn for complete blood count (CBC), Comprehensive Metabolic Panel (CMP, includes a liver panel with AST, ALT, as well as lipids), and high-sensitivity c-reactive protein (hs-CRP). A urine sample for drug screen and pregnancy test (if applicable), psychiatrist assessment, physical exam, collection of weight and vitals will be completed.

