Safety Phone Call (~15 min): Participants will receive a phone call from researchers 7-10 days following their Week 8 study visit (at the end of their tapering schedule). During this phone call, the researchers will assess any withdrawal effects or adverse events and check on the status of the aftercare referrals.

Participants will be paid for their time and inconvenience per visit as follows: \$60 at Baseline 1, Baseline 2, weeks 1, 2, 3, 6; \$70 at week 4; \$90 for week 8. Participants will also be paid for each ISS scale they bring back at the rate of \$1 per scale (maximum \$7). These payments will be processed during Week 1 visit. These payments will be completed via the ClinCard system. Bus or rail passes will be provided. After study completion, standard psychiatric care will be provided until referral is arranged.

Study Medication and Intervention Description:

Participants will be initiated on a 0.5 mg/day brexpiprazole dose (week 0/baseline); after one week the dose will be increased to 1 mg/day (week 1), after another week to 2 mg/day (week 2). If any dose appears to be poorly tolerated, the dose titration can be slowed or stopped based on clinician judgment. If response in weeks 3-6, defined as a 50% reduction in the MADRS, has not been achieved, and the current dose is well tolerated, then additional dose increases to 3 mg/day and 4 mg/day (maximum allowed dose in protocol) will occur with at least a one week interval between dose increases.

Following the last study visit (Week 8), participants will be gradually tapered off the medication every 2 days until they stop taking the medication completely. For example, if a participant takes 4 mg of brexpiprazole at Week 8, then he/she will take 3 mg for 2 days, then 2 mg for 2 days, then 1 mg for 2 days, and then 0.5 mg for 2 days. At the end of the tapering period (7-10 days depending on the highest brexpiprazole dose at the end of the study), participants will receive a safety phone call from a research staff member to assess any withdrawal symptoms and check on the status of the aftercare referrals.

5. Sub-Study Procedures:

No sub-study procedures are anticipated at this time.

6. Criteria for Inclusion of Subjects:

- Outpatient men and women ages 18-65
- Bipolar I or II disorders, currently depressed mood state based on a SCID for DSM-5; Mixed features in DSM-5 are allowed, but those with a Young Mania Rating Scale score ≥ 15 will be excluded
- MADRS score ≥ 25 at baseline 2 visit.

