7. Criteria for Exclusion of Subjects:

- Mood disorders other than bipolar I or II disorders (e.g., bipolar NOS, or cyclothymic disorders, schizophrenia, schizoaffective disorder, or unipolar depression based on the SCID), other disorders, e.g. anxiety disorders, will be allowed
- Current (last 14 days) treatment with an antipsychotic or antidepressant. If a participant has been treated with any antipsychotic or antidepressant in the last 14 days, then they will not be enrolled in the study. No washout of antipsychotic or antidepressant will be done
- History of neuroleptic malignant syndrome or tardive dyskinesia
- Prior history of brexpiprazole use
- Vulnerable populations (e.g., pregnant, nursing, cognitively impaired, incarcerated)

- High risk for suicide defined as > 1 attempt in past 12 months that required medical attention, any attempt in the past 3 months or current suicidal ideation with plan and intent such that outpatient care is precluded
- Severe or life-threatening medical condition, or laboratory or physical examination findings consistent with serious medical illness (e.g., dangerously abnormal electrolytes)
- Moderate or severe hepatic or renal impairment based on medical history and laboratory analyses
- Taking moderate or strong inducers or inhibitors of CYP2D6 or CYP3A4

8. Sources of Research Material:

Clinical information will be obtained via the Structured Clinical Interview for DSM (SCID), Montgomery-Asberg Depression Rating Scale (MADRS), Inventory of Depressive Symptomatology—Self-Report 30-item version (IDS-SR₃₀), Young Mania Rating Scale (YMRS), Columbia Suicide Severity Rating Scale (C-SSRS), Systematic Assessment for Treatment Emergent Effects (SAFTEE), Abnormal Involuntary Movement Scale (AIMS), Barnes Akathisia Scale (BAS), Simpson-Angus Scale (SAS), Ray Auditory Verbal Learning Test (RAVLT), The Stroop and Trail Making Test (TMT).

Biological information will be obtained via blood drawn (2 tbsps ~ 29mLs) for laboratory analyses including a complete blood count (CBC) and Comprehensive Metabolic Panel (CMP, includes a liver panel with AST, ALT, as well as lipids), high-sensitivity c-reactive protein (hs-CRP). A redraw may be requested if the first sample cannot be processed. A physical examination will be performed, weight obtained, and a urine sample collected for a drug screen and pregnancy testing.

9. Recruitment Methods and Consenting Process:

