There are also certain medications that may have clinically significant interactions with brexpiprazole. These medications are moderate or strong inducers or inhibitors of CYP3A4 or CYP2D6. Examples of these medications include, but are not limited to, paroxetine, fluoxetine, quinidine, many HIV medications, etc. A full list of these medications will be made available to participants. This list will also be attached in the IRB application. Participants who currently take moderate or strong inducers or inhibitors of CYP3A4 or CYP2D6 will be excluded from the study. If participants start taking moderate or strong inducers or inhibitors of CYP3A4 or CYP2D6 during their study participation, they will be discontinued from the study and appropriate aftercare referral information will be provided.

Participants will be instructed to let the researchers know of any prescription medications, over-the-counter medications, vitamins and herbal supplements they are currently taking or of ANY new medications they may start taking during their study participation.

Participants will also be informed of potential interaction brexpiprazole may have with alcohol.

Psychological Stress

Some of the questions we will ask you as part of this study may make you feel uncomfortable. You may refuse to answer any of the questions, take a break or stop your participation in this study at any time.

Loss of Confidentiality

Any time information is collected; there is a potential risk for loss of confidentiality. Every effort will be made to keep your information confidential; however, this cannot be guaranteed.

Risks to Sperm, Embryo, Fetus or Breast-fed Infant

Males: Being in this research may damage sperm, which could cause harm to a child that a participant may father while on this study. Subjects who participate in this study and are sexually active, must agree to use a medically-acceptable form of birth control. Medically-acceptable forms of birth control include:

- (1) surgical sterilization (vasectomy), or
- (2) a condom used with a spermicide (a substance that kills sperm).

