All data related to the participant's participation in this study will be given a study ID which cannot be traced back to the patient except by study staff. All personal information which can identify the patient's identity will be kept separately from study documents and assessments. All clinical assessments will be collected in paper form and scores transferred to a computer database maintained on a password protected computer, on a secure server behind a firewall. The paper forms will be kept in binders marked only with the patient's study ID and will be kept in a locked room for the required time period following the completion of this study.

A Certificate of Confidentiality will be obtained for this study.

13. Potential Benefits:

This is a non-randomized open-label clinical trial, thus all participants will receive study medication. All participants may personally benefit from the study by experiencing a significant reduction in symptoms of depression associated with bipolar disorder. The researchers hope the information learned from this study will benefit others with bipolar depression in the future. Information gained from this research could lead to better treatment of patients with bipolar depression.

14. Biostatistics:

Primary Aim: Determine if brexpiprazole is associated with a reduction in depressive symptom severity in outpatients with bipolar disorder, depressed mood state.

1) The MADRS will be the primary outcome measure with the IDS-SR as a secondary outcome measure. Weekly scores on the MADRS and IDS-SR will be assessed using one-way repeated measures. Analysis of Covariance (rm-ANCOVA), controlling for age and sex as potential confounding variables, with time as the main effect. Participants will be included if they complete one post-baseline assessment (intent-to-treat sample). In addition, rates of depression response ($\geq 50\%$ reduction from baseline) and remission (≤ 10 on the MADRS and ≤ 12 on the IDS-SR) will be assessed. A significance level of 0.05 will be set for all analyses, with all tests being two-tailed.

Secondary Aims:

- 2) Assess manic symptoms in patients with bipolar disorder receiving brexpiprazole. YMRS scores will be assessed as with the primary aim above.
- 3) Assess cognition in patients with bipolar disorder receiving brexpiprazole. Scores on the RAVLT, Stroop and TMT will be assessed at baseline compared to weeks 4 and 8 separately using paired t-tests or paired-sample Wilcoxon Signed Rank test.

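### Background mood stabilisers are neither excluded nor required to be stable before Baseline 2, so a recent start or dose change could add to the single-arm MADRS fall

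*Combined protocol and SAP*

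**What the plan says.** Section 7 has two exclusions based on current medication. One is "Current (last 14 days) treatment with an antipsychotic or antidepressant", with no washout allowed. The other is "Taking moderate or strong inducers or inhibitors of CYP2D6 or CYP3A4". Neither Section 6 nor Section 7 mentions mood stabilisers, and neither sets a minimum duration or constant dose for any background drug. The severity requirement is "MADRS score ≥ 25 at baseline 2 visit".

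The Background (Section 2) states: "Lamotrigine is commonly prescribed for bipolar depression, but it appears to be more effective than placebo only for severe depression".

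For the treatment period, Section 10 asks participants to tell the researchers what they currently take and "of ANY new medications they may start taking during their study participation". Only one kind of new drug has a stated consequence: "If participants start taking moderate or strong inducers or inhibitors of CYP3A4 or CYP2D6 during their study participation, they will be discontinued from the study". The general discontinuation list in Section 3 has no item on concomitant drugs. Section 11 deals with drug interactions, not with the effect of other treatments on mood scores.

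The design is a single arm: "We will conduct an 8-week, non-randomized, open label study of brexpiprazole in 20 persons with bipolar disorder". Section 14 tests MADRS with a repeated-measures ANCOVA, "controlling for age and sex as potential confounding variables, with time as the main effect". Background treatment is not a covariate, a stratum or the subject of a sensitivity analysis.

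**The concern.** The protocol keeps recent antidepressants and antipsychotics out of the trial but is silent on a drug that it names itself as commonly prescribed for this condition. A patient who started lamotrigine, or changed its dose, shortly before Baseline 2 is not excluded for that reason.

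With one arm, the primary result is the change over time within participants. A background drug that takes effect over the same 8 weeks would move MADRS in the same direction and over the same period as the study drug. Age and sex are fixed over 8 weeks and say nothing about a recent treatment change, so adjusting for them does not help. What is at stake is how much of the fall can be read as associated with brexpiprazole. As the analysis stands, a reader of the results would not learn how many participants were on another mood treatment or had recently changed it.

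**Working it through.** **Text check.** Taking every place where a rule could stand:

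| Place | Rule on background mood stabilisers |
|---|---|
| Sections 6 and 7, eligibility | None by name; only an agent on the CYP2D6/CYP3A4 list is excluded |
| Section 3, discontinuation list | None |
| Section 10, in-study medications | Report all; only CYP modulators lead to discontinuation |
| Section 14, analysis | Not used |

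The full CYP list is attached to the IRB application and is not in the documents, so which mood stabilisers it would remove cannot be checked.

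**Size.** The plan gives no figure to reproduce: it states 20 participants and a two-sided 0.05 level, but no SD, effect size or power, and no share of participants on mood stabilisers. The following inputs are assumptions:

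- share with a recent start or change, q: 10% to 30%;
- extra MADRS improvement in each of them, e: 3 to 8 points;
- SD of the MADRS change: 8, 10 or 12.

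Inflation of the mean fall = q × e.

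- Low: 0.10 × 3 = 0.3 points.
- High: 0.30 × 8 = 2.4 points.

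**Comparison with the smallest significant mean fall.** A two-sided paired t-test on 20 participants stands in for the ANCOVA time effect. The critical value is t(0.975, 19 df) = 2.093, and the threshold is 2.093 × SD / √20, with √20 = 4.472.

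| Assumed SD | Threshold (points) |
|---|---|
| 8 | 2.093 × 8 / 4.472 = 3.74 |
| 10 | 2.093 × 10 / 4.472 = 4.68 |
| 12 | 2.093 × 12 / 4.472 = 5.62 |

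The high case of 2.4 points lies below all three.

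**Chance of a significant result from this source alone.** Suppose that neither brexpiprazole nor time has any effect and that the expected mean fall is q × e. From the noncentral t distribution with noncentrality (q × e) × √20 / SD, the probability of p < 0.05 is:

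| Mean fall | SD 8 | SD 10 | SD 12 |
|---|---|---|---|
| 0.3 | 0.053 | 0.052 | 0.051 |
| 2.4 | 0.247 | 0.175 | 0.136 |

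The nominal value is 0.05. The effect is negligible at the low end and noticeable at the high end, but even there a significant result from this source alone is unlikely.

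**The case against.** The strongest reply is that this is a proof-of-concept study whose aim claims only an association. Natural course, regression to the mean after a severity floor, and expectation act on all 20 participants. A recent mood-stabiliser change touches, by assumption, a minority. A stability window would not make the time effect causal. All of that stands. It limits the weight of the point but does not remove it, because those other limits come with the design and this one can be avoided.

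Second, medications are already reported, and a psychiatrist sees participants at Baseline 1 and at each post-baseline visit, so some of the information will exist. That also stands. But reporting is not a stability rule, start dates and dose changes are not mentioned, and the analysis does not use the reports.

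Third, mood stabilisers are allowed only by silence. That is correct: the gap is that they are not addressed, not that the protocol expressly permits them.

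Three stronger readings are tempting and are not supported:

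- A reader might infer that background treatment could by itself produce the MADRS fall. The assumed inflation stays below the smallest significant mean fall at every SD tried.
- A reader might infer that it could by itself turn participants into responders. From the entry minimum of 25, a 50% reduction is 12.5 points, more than the assumed 3 to 8.
- A reader might infer that the MADRS floor selects the very patients in whom lamotrigine works. Section 2 is hedged and restrictive about lamotrigine's benefit, and nothing in the documents says that a score of 25 counts as severe in that sense.

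**Conclusion.** The omission is certain from the text. Mood stabilisers outside the CYP list are not excluded, need not be stable before Baseline 2, and are not used in the analysis. A recent start or dose change could therefore add to the MADRS fall that is the primary result.

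The size is not known. The range of 0.3 to 2.4 points rests wholly on the assumed share affected and gain per participant. Within that range, background treatment is a contribution to the fall and not an explanation of it. The bias becomes material only if many participants are affected, and the plan as written would not show how many are.

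This is a cheap improvement, not a flaw that invalidates the study.

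**What to change.** 1. In Section 6 or 7, add a criterion that any permitted background mood stabiliser must not have been started, stopped or changed in dose within a fixed window before Baseline 2. The length of the window is for the sponsor to set.
2. From the medication reports already required in Section 10, record the drug, its start date and every dose change.
3. In Section 14, show MADRS change, response and remission descriptively by background mood-stabiliser use (none versus any). With 20 participants, no subgroup test should be attached.
4. List all background changes during the 8 weeks. If a sensitivity analysis is run, it should not rely on simply dropping those participants: a change after baseline may follow poor response, so removing them can make the remaining improvement look larger. Showing MADRS up to the date of change alongside is one alternative.

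The cost is one eligibility sentence, a few data fields, and one table with a listing. A few candidates would be deferred until stable, which slows recruitment of 20 slightly. Items 2 to 4 can be adopted even if the entry criterion is declined.

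### The 14-day drug look-back names no reference visit and no longer interval for slowly cleared drugs, so a patient recently off fluoxetine can pass both drug exclusions

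*Combined protocol and SAP*

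**What the plan says.** Two criteria in Section 7 (Criteria for Exclusion of Subjects) bear on earlier medication.

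- **Antidepressants and antipsychotics.** "If a participant has been treated with any antipsychotic or antidepressant in the last 14 days, then they will not be enrolled". The same 14 days apply to every drug in both classes. No reference visit is named, and the study does not manage any washout.
- **CYP modulators.** The criterion reads "Taking moderate or strong inducers or inhibitors of CYP2D6 or CYP3A4", with no look-back. Section 10 (Potential Risks) repeats it in the present tense: "Participants who currently take moderate or strong inducers or inhibitors of CYP3A4 or CYP2D6 will be excluded from the study". On the drugs concerned, Section 10 says: "Examples of these medications include, but are not limited to, paroxetine, fluoxetine, quinidine, many HIV medications, etc". It also refers to a full list attached to the IRB application. The withdrawal rule there applies only to new use: "If participants start taking moderate or strong inducers or inhibitors of CYP3A4 or CYP2D6 during their study participation".

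Section 11 (Subject Safety and Data Monitoring) says that drug interactions will be handled through the eligibility and discontinuation criteria and through dose adjustments. It leaves the question of whether a participant can safely continue to physician judgment.

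Under Section 4, dosing starts at Baseline 2 with 0.5 mg/day and rises to 1 mg at Week 1 and 2 mg at Week 2, if tolerated. Section 14 (Biostatistics) uses every visit: "Weekly scores on the MADRS and IDS-SR will be assessed using one-way repeated measures". The safety scales are analysed in the same way.

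**The concern.** The two criteria leave a gap between them. Paroxetine and fluoxetine are antidepressants as well as named CYP modulators, so the 14-day rule catches recent use of either. After 14 days neither criterion applies, however slowly the drug is cleared. Fluoxetine is the natural test case. Section 10 names it, and prior use is plausible in this population because Section 2 says: "Only three medications (quetiapine, the combination of olanzapine and fluoxetine, and lurasidone) are FDA-approved for bipolar depression".

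Two things would be at stake if a relevant amount of drug remained. First, brexpiprazole exposure could be altered during the fourfold rise from 0.5 to 2 mg/day. Second, residual drug could overlap the ratings at Baseline 2 and the early visits (SAFTEE, AIMS, BAS, SAS and MADRS). With no control arm, its contribution could not be told apart from that of brexpiprazole.

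**Working it through.** **Step 1: do the criteria let such a patient in?** The plan gives no figure to reproduce here, so this step is a reading of the text. Take a patient whose last fluoxetine dose was 15 days before the reference visit.

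- Antidepressant rule: 15 > 14, so it is not triggered.
- CYP rule: the patient no longer takes the drug, so it is not triggered.
- On-study rule in Section 10: nothing has been started, so it is not triggered.
- Section 11: it gives no look-back and no dose rule for a recently stopped inhibitor.

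**Step 2: does the reference visit matter?** Let Baseline 1 fall g days before Baseline 2; the protocol does not give g. If the site counts from Baseline 1, a patient 15 days off drug at Baseline 2 is only 15 − g days off at the count. That is 14 (borderline) for g = 1 and 8 (excluded) for g = 7. A patient 15 days off at Baseline 1 still passes, but is 15 + g days off at the first dose. So the gap exists under either reading, and counting from Baseline 1 makes the residual smaller.

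**Step 3: how much drug could remain?** The documents give no half-life. Assume 4, 7 or 16 days for fluoxetine including its active metabolite. Percent remaining = 100 × 0.5^(days ÷ half-life). The table takes day 15 as Baseline 2, so days = 15 + 7 × week.

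| Visit (brexpiprazole dose) | Day | 4 d | 7 d | 16 d |
|---|---|---|---|---|
| Baseline 2 (0.5 mg) | 15 | 7% | 23% | 52% |
| Week 1 (1 mg) | 22 | 2% | 11% | 39% |
| Week 2 (2 mg) | 29 | 0.7% | 6% | 28% |
| Week 4 | 43 | 0.1% | 1% | 16% |
| Week 8 | 71 | <0.001% | 0.1% | 5% |

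If g = 7 and the site counts from Baseline 1, the first dose falls on day 22, and the second row gives the residual at that dose.

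Break-even: 5% or less remains at day 15 only if the half-life is at most 15 × ln 2 ÷ ln 20 = 3.5 days.

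**Step 4: what could this do to the efficacy results?** The number of such patients is unknown. Suppose one of 20 is affected, with an assumed carry-over of 5 or 10 MADRS points at a visit. The group mean at that visit moves by 5 × 1 ÷ 20 = 0.25 or 10 × 1 ÷ 20 = 0.5 points. One changed responder moves the response rate by 1 ÷ 20 = 5 percentage points.

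**Step 5: how long would a 5-half-life interval be?** The residual is 0.5^5 = 3%. The interval is 5 × 4 = 20, 5 × 7 = 35 or 5 × 16 = 80 days. It exceeds the existing 14 days only for drugs with a half-life above 14 ÷ 5 = 2.8 days.

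**The case against.** The strongest reply is that the decisive premise is not in the documents. Section 10 says that fluoxetine interacts. No section says how long it or its metabolite persists, or how long CYP inhibition lasts after stopping. That stands. At the 4-day end of the range there is little to correct.

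A reader might infer that a patient 15 days off fluoxetine at Baseline 2 is certain to be admitted. The text does not support that, because a site counting from an earlier Baseline 1 could exclude this patient (Step 2).

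A reader might also infer that the rules fail at their own purpose. But Section 7 is directed at current or recent treatment and does not claim to exclude residual drug. A uniform window is a legitimate design choice.

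Safeguards exist. Titration can be slowed or stopped when a dose is poorly tolerated, a psychiatrist sees the participant at each post-baseline visit, and Section 11 allows dose adjustment and physician judgment. The IRB list, which is not available here, may already give timing. These points soften the safety concern. None of them sets an interval, and the option to slow titration responds to a problem that has already appeared.

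Finally, any efficacy effect is small beside the absence of a control arm. That stands too. Every participant must still score at least 25 on the MADRS at Baseline 2, and Section 2 itself doubts that SSRIs work well in bipolar depression.

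**Conclusion.** The gap in the eligibility text is real and needs no assumption: a patient more than 14 days off fluoxetine at the reference visit passes both criteria, and nothing else in the protocol closes the gap. Its importance does depend on an assumption. With half-lives of 4 to 16 days, the residual at day 15 runs from 7% to 52%, and at the 2 mg step from 0.7% to 28%. The concern is negligible at the short end. At the long end it is a reasonable one for brexpiprazole exposure and early tolerability ratings.

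Residual fraction is not clinical effect, and the documents do not show that inhibition persists or that exposure changes. Nor do they support reading this as a material bias in the primary result. With one affected patient the shift in a visit mean is 0.25 to 0.5 points under the assumed carry-over. Its direction is unknown, and it would arise mainly at early visits rather than at Week 8. This is a cheap, optional improvement of low severity.

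**What to change.** In Section 7:

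1. Count the look-back from the first brexpiprazole dose (Baseline 2).
2. Keep 14 days as the default. Set a longer interval, stated in days, for fluoxetine and fluoxetine-containing combinations, and for any other listed drug whose 5 half-lives (active metabolites included) exceed 14 days. The sponsor must take the half-lives from its own pharmacology sources, since the protocol gives none.
3. Reword the CYP criterion to *taking, or stopped within the listed interval of*, followed by the existing drug classes, with the intervals given in the list attached to the IRB application. If that list already gives timing, cite it in the criterion.

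The policy of not washing anyone out for the study stays as it is.

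The cost is a few reworded eligibility lines and some entries in an existing list. The downside is that a few candidates for a 20-person study are deferred or excluded. On the assumed half-lives, a patient at day 15 would wait a further 5, 20 or 65 days. Anyone facing a long deferral should be referred for usual care rather than held untreated.
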